7.4 Concomitant or Prohibited Therapy

No investigational product will be administered during this long-term follow-up study. Unmasking procedures are not pertinent to this study as no study treatment/study procedures will be performed during the long-term follow-up.

No intervention specific for LHON, the disease under study, will be allowed during this long-term follow-up study and subjects will not be permitted to enroll in any investigational trials.

Subjects may receive concomitant medications that are for indications other than the treatment of vision loss due to LHON, and these are allowed per the decision and discretion of the Investigator.

Idebenone (Raxone[®]; approved in Europe for LHON, but not in the US) will be prohibited during the study. If the subject starts idebenone during the long-term follow-up, this will be considered non-adherence to the protocol but will not disqualify the subject from continuing in the study.

Any other treatments that are considered necessary for the subject's welfare may be given at the discretion of the Investigator. Administration of concomitant medications must be reported in the appropriate section of the eCRF along with dosage information, dates of administration, and reasons for use. Generic names for concomitant medication should be used, if possible. The total daily dose should be filled in whenever possible.

7.5 Safety, Efficacy, and Quality-of-Life Variables

7.5.1 Safety Variables

The safety variables in this study will be AEs and SAEs.

7.5.2 Efficacy Variables

The efficacy variables in this study will be contrast sensitivity; BCVA reported in LogMAR; parameters of HVF and SD-OCT; and general and vision-specific parameters affecting QOL (see Section 7.5.3).

7.5.3 Quality-of-Life Variables

The general overall QOL variables are physical, social, and emotional functioning, bodily pain, mental health and general health perceptions, and vitality/energy, as judged by the subject.

The vision-specific QOL variables are eyesight, eye discomfort, ability to read, seeing close objects, seeing distant objects, nighttime vision, seeing during movement/motion, peripheral vision, color vision, and effect of vision on work activities, as judged by the subject.

8. STUDY ASSESSMENTS AND PROCEDURES BY VISIT

8.1 Informed Consent

After the study has been fully explained, written informed consent will be obtained from either the subject or his/her guardian or legal representative prior to study participation. The method of obtaining and documenting the informed consent and the contents of the consent will comply with International Council for Harmonisation (ICH) GCP and all applicable regulatory requirement(s). Since this study will be collecting long-term follow-up assessments, the informed consent must include the expected duration of the subject's participation and the time intervals between site visits.

Logistically, the informed consent will be obtained prior to performing any study related procedures or documenting any subject data in the eCRF. If the subject does not want to commit to enrolling in the long-term follow-up study during the last visit (W96) of the RESCUE/REVERSE study, then subject may have up to 1 day prior to Visit 2 to sign the informed consent form (ICF). It will be explained and agreed to by the subject as part of the informed consent that assessment data from the RESCUE/REVERSE clinical database may be used as needed in order to complete the required data summaries and statistical analyses for the long-term follow-up study.

It will be recommended that the subject inform their primary physician about their participation in the RESCUE/REVERSE long-term follow-up study.

8.2 Schedule of Events

The Schedule of Events (**Table 1**) provides the procedures/assessments to be performed at each scheduled visit for long-term follow-up period.

The inclusion assessments may be performed at the Week 96/EOS visit of RESCUE/REVERSE and up to 1 day prior to the Visit 2 (Year 2.5 visit [up to 180 days post Week 96]).

Table 1: Schedule of Events

Years post-treatment	Inclusion Period	Long-term Follow-up Period			
	Year 2 (Week 96) ^a	Year 2.5 (± 4 weeks)	Year 3 (± 4 weeks)	Year 4 (± 4 weeks)	Year 5 EOS (± 4 weeks) ^b
Procedure	Visit 1	Visit 2	Visit 3	Visit 4	Visit 5
Informed consent	X				
Clinical Assessments/Procedures					
Review inclusion/exclusion criteria	X				
Medical history	X				
Physical examination including vital signs ^c	X				X
Electrocardiogram (12-lead)	X				X
Review concomitant medications	X	X	X	X	X
Adverse events/serious adverse events ^d	X	X	X	X	X
Laboratory Assessments					
Hematology/serum chemistry including liver function ^e	X				X
Quality of Life Assessments					
VFQ-25 ^f	X		X	X	X
SF-36 ^f	X		X	X	X
Ocular and Vision Assessments					
Slit-lamp examination ^g	X	X	X	X	X
Goldmann applanation tonometry for intraocular pressure ^h	X	X	X	X	X
Refraction for BCVA	X	X	X	X	X
Visual Acuity (ETDRS)	X	X	X	X	X
Humphrey TM visual field 30-2	X	X	X	X	X
Pelli-Robson contrast sensitivity ^h	X		X	X	X
SD-OCT	X	X	X	X	X
Color fundus photography	X	X	X	X	X

Abbreviations: BCVA, best-corrected visual acuity; EOS, End of Study; ETDRS, Early Treatment Diabetic Retinopathy Study; SD-OCT, spectral domain optical coherence tomography; SF-36v2, 36-item Short Form Health Survey; VFQ-25, Visual Function Questionnaire-25, version 2.

^a The inclusion window will be from Week 96 visit up to 1 day prior to Visit 2, which will be approximately 180 days post W96/EOS.

^b Subjects who discontinue participation in the long-term follow-up study prematurely (i.e., prior to Visit 5) will complete an EOS visit, including Visit 5 procedures.

- ^c Examination includes general appearance, skin, head, eyes, ears, nose, throat, neck, thyroid, chest/lungs, heart, abdomen, lymph nodes, extremities, and body weight and height. Vital signs include temperature, pulse rate, and systolic and diastolic blood pressure.
- ^d Record in the eCRF any AE that is causally related to study medication and/or study procedure, any ocular AE (causally related or unrelated to study medication and/or study procedure), and any SAE (causally related or unrelated to study medication and/or study procedure).
- ^e Refer to laboratory instruction manual for sample processing. Record in the eCRF any clinically significant abnormality, by parameter name and value, if deemed causally related to study medication and/or study procedure.
- ^f Conduct after AE assessment and prior to visual acuity testing.
- ^g Perform examination before and after pupil dilation.
- ^h Perform examination before pupil dilation.

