9.4 Clinical Laboratory Testing

Venous blood samples will be taken for hematology and chemistry testing at Visit 1 and Visit 5 (EOS) or ETV. The following parameters will be determined:

- Hematology: complete blood count including red blood cells, hemoglobin, hematocrit, white blood cells with differential counts, and platelets.

- Serum chemistry: glucose, lipase, amylase, calcium, sodium, potassium, chloride, bicarbonate, blood urea nitrogen (BUN), and creatinine.
- Liver Function Tests: aspartate aminotransferase (AST), alanine aminotransferase (ALT), alkaline phosphatase (ALP), gamma-glutamyl transpeptidase (γ GT), total bilirubin, and albumin.

Analysis of samples will be conducted by the study central laboratory. Further details of the procedures to be followed for sample collection, storage, and shipment will be documented in a Laboratory Manual.

Additional and repeat laboratory safety testing may be performed at the discretion of the Investigator.

The Investigator, or designee, is responsible to review the results of all laboratory tests in a timely manner. For all abnormal values, the Investigator must provide comments on the laboratory results sheet, identifying those that are abnormal and clinically significant, as well as those that are abnormal and not clinically significant. A clinically significant abnormal finding that is causally related to the IMP will be reported as an AE as per the Investigator's judgment.

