11.5 Statistical Methods

11.5.1 Safety Analyses

Primary Safety Analysis

Adverse events and SAEs related to GS010 IVT injection or study procedure will be summarized in two different ways: (1) systemic AEs and SAEs related to study drug/procedure, and (2) ocular AEs and SAEs related to study drug/procedure. Systemic AE data will be summarized by all subjects. Ocular AE data will be summarized by sham eye only and GS010 eye only.

Clinically significant abnormal findings observed during physical examination, vital signs measurement, ECG recording, or laboratory values will be summarized as AEs in the AE tables if the clinically significant abnormal finding is deemed as causally related to the study medication or study procedure.

The following summaries will be produced for (1) SAEs unrelated to study drug/study procedure, (2) systemic AEs/SAEs related to study drug/procedure, and (3) ocular AEs/SAEs related to study drug/study procedure, using counts and percentage as follows:

- Overall summary of AEs/SAEs related to study drug/procedure
- AEs related to GS010 IVT injection or study procedure, including the number of events reported
- AEs/SAEs related to GS010 IVT injection or study procedure by maximum severity
- AEs/SAEs related to GS010 IVT injection or study procedure leading to study discontinuation
- SAEs related to GS010 IVT injection or study procedure
- SAEs related to GS010 IVT injection or study procedure leading to death.

Events will be coded using the MedDRA and summarized by system organ class and preferred term.

Secondary Safety Analysis

The number, type, frequency, and severity of ocular or vision-related AEs, including those with no relation or any relation to the GS010 IVT injection or study procedure will be presented in the same way that the primary endpoint of ocular AEs/SAEs related to GS010 IVT injection or study procedure.

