8.6.2 Laboratory Data

Parameters analyzed by the central laboratory will be used for statistical analysis. The laboratory test includes the following:

- Hematology tests and other blood laboratory tests: Complete blood count including red blood cells, hemoglobin, hematocrit, white blood cells with differential counts and platelets.
- Blood chemistry tests: Glucose, lipase, amylase, calcium, sodium, potassium, chloride, bicarbonate, blood urea nitrogen (BUN) and creatinine.
- Liver function tests: AST, ALT, ALP, γ GT, total bilirubin and albumin

The statistical analysis of clinical laboratory tests will be conducted as described below.

Descriptive analysis (number of subjects, mean, SD, median, Q1, Q3, minimum, maximum) of each parameter at each time point and the changes from baseline;

Individual data listings of laboratory results will be presented for each subject at all study visits (scheduled and non-scheduled), including normal range limits for each laboratory test.

Out-of-range results will be flagged, and determinations of whether the results were considered to be of clinical significance by the investigator will be included. Clinically significant abnormal lab values for different parameters will be summarized at each post baseline time point.

Additionally, a summary will be presented of subjects who had an out-of-range result, including the subject, visit date, baseline value, normal range and out-of-range value observed.

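### Table 1 footnote e admits clinically significant laboratory abnormalities to the eCRF only if judged related, while SAP 8.6.2 tabulates them with no such condition

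*Protocol*

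**What the plan says.** - **Protocol 8.2, Table 1, footnote e**, on the laboratory row: "Record in the eCRF any clinically significant abnormality, by parameter name and value, if deemed causally related to study medication and/or study procedure". The SAP repeats the footnote in its own Table 1 (Section 3.2).
- **Protocol 9.4** has blood drawn at Visit 1 and at Visit 5 or early termination, and the investigator rates every abnormal result whatever its cause: "For all abnormal values, the Investigator must provide comments on the laboratory results sheet, identifying those that are abnormal and clinically significant". Relatedness comes in only afterwards, for adverse event reporting: "A clinically significant abnormal finding that is causally related to the IMP will be reported as an AE".
- **SAP 8.6.2** takes its parameters from the central laboratory, flags out-of-range results and includes the investigator's judgement of their clinical significance. It then states: "Clinically significant abnormal lab values for different parameters will be summarized at each post baseline time point". Neither statement depends on relatedness. The same section plans descriptive statistics with change from baseline, individual listings with normal ranges, and a summary of subjects with an out-of-range result.
- **Protocol 11.1** names the eCRF and electronic data capture as the means of data collection.
- **SAP 8.8**, which lists departures from the protocol, does not mention this point.

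**The concern.** The entry rule and the analysis rule do not cover the same findings. Footnote e asks for significant abnormalities judged related. SAP 8.6.2 asks for all significant abnormalities. If sites follow the footnote, the analysis may lack the significance call for findings judged unrelated, yet nothing in the table's description would tell a reader that it had been filtered.

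Long-term safety is the primary objective, and the protocol's rationale (5.3) includes finding delayed events and long-term risks not yet explored. For that purpose it helps to see significant laboratory changes before the investigator's causality judgement is applied. Scheduled sampling occurs at only two visits, and no data monitoring committee reviews the results. A reader would probably take a table of clinically significant values as complete. A significant liver or blood-count change at Year 5 that was judged unrelated might then be visible only as an out-of-range number.

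**Working it through.** No sample size, error rate or laboratory event rate is stated for this point, so there is no figure in the plan to reproduce. The check follows a laboratory result from sample to table.

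**Step 1. Numeric values.** Protocol 9.4: "Analysis of samples will be conducted by the study central laboratory". SAP 8.6.2 analyses those values. This stream has no causality filter and feeds the descriptive statistics, the listings and the out-of-range summary.

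**Step 2. Significance call.** A central laboratory supplies values and reference ranges. Clinical significance is the investigator's judgement, so it needs its own route into the data. Protocol 9.4 places the call on the laboratory results sheet for every abnormal value.

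**Step 3. From sheet to database.** Protocol 11.1 describes electronic capture, and 12.1 and 13.1 have site staff enter data from source documents. The only rule in either document for moving a significant laboratory abnormality into the eCRF is footnote e, and it admits related findings only. No route is described for the significance call on an unrelated finding.

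**Step 4. Adverse events as a safety net.** Protocol 9.4 and 10.5.1 make a significant laboratory finding an adverse event only if related. Protocol 11.5.1 does the same for the tables: "or laboratory values will be summarized as AEs in the AE tables if the clinically significant abnormal finding is deemed as causally related". Under 10.1.2 the eCRF records related events, ocular or vision-related events, and serious events of any cause. An unrelated laboratory finding that is serious is therefore still recorded as an SAE. One that is not serious is not recorded as an adverse event.

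**Step 5. Result for each kind of significant laboratory finding, on the documented path:**

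| Finding | Numeric outputs | Significance table and listing column | Adverse event tables |
|---|---|---|---|
| Related | Shown | Shown | Shown |
| Unrelated, serious | Shown | No route described for the call | Shown as SAE |
| Unrelated, not serious | Shown | No route described for the call | Not shown |

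**Step 6. Size.** Let r be the share of clinically significant laboratory abnormalities judged related. The documents do not give r, so the values below are assumptions spanning its full range.

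- If footnote e is the only source of the call, share shown = r and share omitted = 1 − r.
- If the call on the results sheet is captured for every abnormal value, share shown = 100% and share omitted = 0, whatever r is.

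| r (assumed) | Omitted, footnote e only | Omitted, sheet captured in full |
|---|---|---|
| 0 | 100% | 0% |
| 0.1 | 90% | 0% |
| 0.5 | 50% | 0% |
| 1 | 0% | 0% |

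The documents do not settle which column applies.

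**The case against.** The strongest reply is that footnote e is an adverse event rule rather than a rule for laboratory data. Its condition matches the one in Protocol 9.4, 10.5.1 and 11.5.1, where relatedness decides only whether a finding becomes an adverse event. It also cannot govern all laboratory data, since SAP 8.6.2 summarises every parameter and lists every result. ECG shows that the two can coexist: under Protocol 9.3 only related significant findings become adverse events, yet SAP 8.6.4.2 tabulates normal, significant and non-significant findings by visit. The eCRF, the Data Management Plan and the Laboratory Manual are not among the documents, and the eCRF may already hold a significance field for every abnormal value.

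Much of this stands. A reader might infer that the SAP table shows only related findings, that unrelated calls never reach the database, or that the plan understates laboratory toxicity. The documents support none of these as fact. SAP 8.6.2 contains no causality filter, the actual capture route cannot be seen, and three kinds of output report abnormal values regardless of cause. Any specific percentage of missing findings would be a guess.

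The reply does not remove the conflict. Footnote e speaks of recording the abnormality by parameter and value and does not mention adverse events, whereas footnote d on the adverse event row has its own recording rule. The ECG row has no comparable footnote. Citing central-laboratory data does not supply an investigator's judgement. If the adverse event reading is the intended one, the text should say so.

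**Conclusion.** The conflict between footnote e and SAP 8.6.2 is real and should be resolved. On the only path the documents describe, one table and the significance column of the listing would omit non-serious significant laboratory findings judged unrelated, and the adverse event tables would not make up for it.

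The consequence is limited. Numeric values are reported in full, unrelated SAEs are still captured, and the primary endpoint, which concerns related events, is unaffected. The omission could be anything from 0 to 100% and cannot be narrowed from the documents. The conclusion assumes that sites follow footnote e as written and that no undocumented route carries the significance call. If the eCRF already captures every call, only the wording is at fault.

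**What to change.** Reconcile footnote e in both Table 1s with Protocol 9.4 and SAP 8.6.2:

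1. For every abnormal central-laboratory value, enter in the eCRF the clinical-significance call already required on the laboratory results sheet. Record relatedness in a separate field.
2. Name that source in SAP 8.6.2.
3. Tabulate all clinically significant values by parameter and time point, with the related subset beneath.
4. If the calls for unrelated values cannot be retrieved, label the table and the listing column as related findings only.

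If the eCRF already holds the call for every abnormal value, correcting footnote e, naming the source and adding the related subset to the table are enough. The cost is a small transcription effort at two scheduled visits per subject, and a table that shows more abnormalities.

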8.3 Visit 1: Inclusion Period (Year 2)

The Inclusion Period will start on the date of the last visit (W96) of the RESCUE/REVERSE study and end 1 day prior to Visit 2 (Year 2.5, Day 179) of the long-term follow-up study.

Ideally, the Visit 1 should be combined with the Week 96/EOS visit of RESCUE/REVERSE. If this is not possible, a separate Visit 1 will be scheduled during the Inclusion Period to sign the informed consent, review eligibility criteria, review AEs/SAEs and concomitant medications, and perform any additional assessments that were not completed during the Week 96/EOS visit of RESCUE/REVERSE.

The following assessments will be performed during the Inclusion Period in the approximate order listed:

- Review and update medical, surgical, and prior medication history
- Physical examination and vital signs
- Review of inclusion/exclusion criteria
- Review concomitant medication
- AEs/SAEs
- Clinical laboratory testing (hematology and serum chemistry including liver function)
- ECG
- VFQ-25 questionnaire
- SF-36v2 questionnaire
- Ocular and vision assessments
 - Refraction for BCVA, performed prior to pupil dilation
 - Visual acuity assessment, performed prior to pupil dilation
 - HVF 30-2, performed prior to pupil dilation
 - Goldmann applanation tonometry for intraocular pressure (IOP) measurement, performed prior to pupil dilation
 - Pelli-Robson contrast sensitivity, performed prior to pupil dilation
 - Slit-lamp examination (SLE) performed pre- and post-pupil dilation
 - SD-OCT, performed after pupil dilation

- Color fundus photography after pupil dilation.

8.4 Visit 2: Year 2.5 (\pm 4 Weeks) Post-treatment

The following assessments/procedures will be performed:

- Review concomitant medication
- Adverse events/SAEs
- Ocular and vision assessments
 - Refraction for BCVA, performed prior to pupil dilation
 - Visual acuity assessment, performed prior to pupil dilation
 - HVF 30-2, performed prior to pupil dilation
 - Goldmann applanation tonometry for IOP measurement, performed prior to pupil dilation
 - SLE performed pre- and post-pupil dilation
 - SD-OCT, performed after pupil dilation
 - Color fundus photography after pupil dilation.

8.5 Visit 3: Year 3 (\pm 4 Weeks) Post-treatment

- Review concomitant medication
- Adverse events/SAEs
- VFQ-25 questionnaire
- SF-36v2 questionnaire
- Ocular and vision assessments
 - Refraction for BCVA, performed prior to pupil dilation
 - Visual acuity assessment, performed prior to pupil dilation
 - HVF 30-2, performed prior to pupil dilation
 - Goldmann applanation tonometry for IOP measurement, performed prior to pupil dilation

- Pelli-Robson contrast sensitivity, performed prior to pupil dilation
- SLE performed pre- and post-pupil dilation
- SD-OCT, performed after pupil dilation
- Color fundus photography after pupil dilation.

8.6 Visit 4: Year 4 (\pm 4 Weeks) Post-treatment

- Review concomitant medication
- AEs/SAEs
- VFQ-25 questionnaire
- SF-36v2 questionnaire
- Ocular and vision assessments
 - Refraction for BCVA, performed prior to pupil dilation
 - Visual acuity assessment, performed prior to pupil dilation
 - HVF 30-2, performed prior to pupil dilation
 - Goldmann applanation tonometry for IOP measurement, performed prior to pupil dilation
 - Pelli-Robson contrast sensitivity, performed prior to pupil dilation
 - SLE performed pre- and post-pupil dilation
 - SD-OCT, performed after pupil dilation
 - Color fundus photography after pupil dilation.

8.7 Visit 5: Year 5 (\pm 4 Weeks) Post-treatment (EOS) or (ETV)

- Review concomitant medication
- Adverse events/SAEs
- Physical examination and vital signs
- Clinical laboratory testing (hematology and serum chemistry including liver function)
- ECG

- VFQ-25 questionnaire
- SF-36v2 questionnaire
- Ocular and vision assessments
 - Refraction for BCVA, performed prior to pupil dilation
 - Visual acuity assessment, performed prior to pupil dilation
 - HVF 30-2, performed prior to pupil dilation
 - Goldmann applanation tonometry for IOP measurement, performed prior to pupil dilation
 - Pelli-Robson contrast sensitivity, performed prior to pupil dilation
 - SLE performed pre- and post-pupil dilation
 - SD-OCT, performed after pupil dilation
 - Color fundus photography after pupil dilation.

An early termination visit will include the EOS assessments.

